Although Non-contrast CBBCT has received FDA PMA approval, FDA requires a separate PMA submission to prove the safety and effectiveness of CE-CBBCT within diagnostic population. A multi-reader multi-case (MRMC) pivotal reader study has been designed to compare CE-CBBCT+2-view mammograms to diagnostic mammography, the primary modality in diagnostic workup, to prove the hypothesis that CE-CBBCT is superior to diagnostic mammography in the diagnosis of breast cancer. Previous studies acquired only BIRADS 4 and 5 patients. New acquisition study is necessary so that the final database used for the MRMC study can cover the full diagnostic population of breast cancer.

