6.1 CE-CBBCT PROCEDURE

The subjects will first have a pre-contrast CBBCT scan. Iodinated contrast will be injected intravenously, and then another CBBCT scans will be performed to capture the tumor vasculature enhancement. Features to look for are degree of enhancement pattern of the lesion as compared to surrounding pattern. Delay times and contrast volume/rate will be determined initially through previous CT studies then optimized through this CBBCT study. Each CBBCT scan takes 10 seconds and delivers a glandular dose similar to a diagnostic mammography exam. State board-certified and Mammography Quality Standards Act (MQSA) qualified mammographers will evaluate the CBBCT high resolution 3D images and compare them to the subjects' mammograms. If the subject had an MRI or ultrasound, then these would be compared as well. If the patient's diagnostic outcome is BIRADS 4 and above and has biopsy or surgery, pathology will provide final confirmation. If the patient's diagnostic outcome is BIRADS 1, 2, 3, follow up results will provide final confirmation.

Physicians familiar with contrast-enhanced multislice CT procedures will be available during the CE-CBBCT procedures and will advise on modifications.

Once all the projections are acquired, projections will then be used for volume reconstruction. Since a malignant tumor has many blood vessels, it will be enhanced in the post-contrast reconstructed image. The contrast enhancement of the malignant tumor will be quantified by CT number measurements. To explore dynamic contrast-enhanced vasculature patterns (wash-in, wash-out), we propose to select the scan at various delay times on different subjects with similar lesions to see if we can get preliminary data on this functional effect while keeping the dose to individual subjects low.

The radiographic technique will be 49 kVp, 8 ms/projection image, and 300 images per scan. The mA will be automatically selected by the CBBCT system from 50 to 160 mA, depending on size and density of the breast. This translates to a range of average glandular dose to the breast from ~4

Clinical Trial Protocol			
Title:	Contrast-Enhanced Cone Beam Breast CT for Diagnostic Breast Imaging		
Internal #:	16-01		
IRB #:	RSRB00061893	NCT #:	NCT03354611
Revision:	3.5	Effective Date:	

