Two MQSA qualified board-certified mammography radiologists will evaluate the CE-CBBCT study along with all prior imaging and histological results to determine the added value of CE-CBBCT. Initially, the radiologists will review the CE-CBBCT images and make independent diagnostic decisions blindly from MRI and ultrasound image results, if available. Next, they will compare the results of CE-CBBCT to diagnostic mammography, non-contrast CBBCT, MRI, and ultrasound images. Finally, they will compare their findings for each case to histological results, which are considered to be the quantitatively gold standard in diagnosis. The comparison will answer three questions:

1. Can the CE-CBBCT detect lesions that not detected by other modalities?
2. Can the CE-CBBCT better distinguish between benign and malignant masses?
3. Can the CE-CBBCT help show the extent of disease?

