7 DATA RECORDING

Information to be recorded on the participants includes:

- Subject age
- Date of Birth
- Height and weight
- Ethnic category
- Body habitus
- Measurement of breast
- Information to be recorded about imaging
 - Date of breast imaging studies
 - Date of CE-CBBCT imaging
- Pertinent clinical information, imaging data, interpretation data, and biopsy data will be recorded by hand through data sheets (CRF 1-13). All data will be subsequently entered into Excel spreadsheets to track results.

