9 ANALYSIS OF RESULTS

All data will be collected in a spreadsheet.

Contrast-enhanced CBBCT (CE-CBBCT) for breast imaging will be evaluated, tabulated, and analyzed in terms of lesion conspicuity and detail in comparison with the non-contrast CBBCT exam, mammogram, and contrast-enhanced breast MRI. We will evaluate wash in and wash out patterns and degree of enhancement of the lesion as compared to surrounding pattern.

Demographic and clinical characteristics of the study population will be described using mean and standard deviation for quantitative variables such as age, or percentage and percentiles for qualitative variables such gender, race, and cancer staging.

Reported adverse events will be tabulated according to its description, severity, and relationship to the specific imaging or clinical procedures. All patients will be included in the safety analysis.

Paired t-test (for quantitative measurements such as tumor size, time of wash in and wash out) or McNemar's test (for qualitative data such as type of mass, type of calcification) will be used for comparisons between the CE-CBBCT and other modalities.

Accuracy of diagnosis will be evaluated in terms of sensitivity and specificity by comparing the test results from each imaging modality to that of the biopsy (the gold standard). When sufficient data is available, comparisons between CE-CBBCT and the other modalities will then be conducted using McNemar's test.

No imputation will be used for missing data (i.e., only patients who have the specific data available will be included in a particular analysis.) Statistical analysis will be performed using SAS (SAS Institute, Cary, N.C., U.S.A.). All tests will be 2-sided with the confidence level set to 95%.

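### Section 9 takes biopsy as the only truth for sensitivity and specificity, so unbiopsied BIRADS 1–3 women, whom Section 6.1 confirms by follow-up, drop out of the accuracy comparison (partial verification bias)

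*Protocol*

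**What the plan says.** The protocol sets the reference standard in three places.

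- **Section 6.1 (CE-CBBCT procedure)** uses two standards. For the higher categories: "If the patient's diagnostic outcome is BIRADS 4 and above and has biopsy or surgery, pathology will provide final confirmation". For the lower ones: "If the patient's diagnostic outcome is BIRADS 1, 2, 3, follow up results will provide final confirmation".
- **Section 9 (Analysis of results)** uses one. Sensitivity and specificity are obtained "by comparing the test results from each imaging modality to that of the biopsy (the gold standard"; follow-up is not mentioned. McNemar's test then compares CE-CBBCT with the other modalities if there are enough data. Nothing is imputed, and "only patients who have the specific data available will be included in a particular analysis".
- **Section 6.3.3 (Review of the CE-CBBCT)** also uses one. The two radiologists finally check each case against "histological results, which are considered to be the quantitatively gold standard in diagnosis".

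Biopsy is done only when needed (Sections 5.1 and 6), and Sections 4, 5.1 and 5.3 call for BIRADS 1, 2 and 3 cases. On data capture, Section 7 states that "imaging data, interpretation data, and biopsy data will be recorded by hand through data sheets (CRF 1-13"; Section 8 lists pathology reports. Neither names a follow-up outcome.

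**The concern.** A BIRADS 1–3 woman who is never biopsied has a confirmed status under Section 6.1 but no reference result under Section 9. The available-case rule then removes her from the sensitivity and specificity denominators and from McNemar's test.

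This is more than lost precision. Whether a woman is verified depends largely on the result of the work-up that is being compared with CE-CBBCT. Suppose BIRADS 4 or above counts as positive (an assumption; Section 9 gives no cut-off). Restricting to biopsied women then pushes the combined work-up call towards 100% sensitivity and 0% specificity. Mammography read alone moves the same way without being fixed there. The comparison therefore tends to show CE-CBBCT gaining specificity and losing sensitivity, whatever it does in BIRADS 1–3 women.

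Section 1.2 justifies the new acquisition on the ground that "Previous studies acquired only BIRADS 4 and 5 patients". An accuracy analysis confined to biopsied women goes largely back to that group.

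**Working it through.** The protocol gives no sensitivity, specificity, power or sample size for this comparison, so there is no stated figure to reproduce. The check is of the text, followed by an illustration of size.

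**Who is left out**

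| Patient | Final confirmation, Section 6.1 | Reference result, Section 9 | In the accuracy analysis? |
|---|---|---|---|
| BIRADS ≥4, biopsy or surgery | pathology | biopsy | yes |
| BIRADS 1–3, biopsied by another route | follow-up | biopsy | yes |
| BIRADS 1–3, not biopsied | follow-up | none | no |

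No section carries the follow-up result into the accuracy analysis.

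**How many.** From the protocol: 100 patients, at least 30 cancers (Sections 2 and 3), and an earlier yield of 38 cancers in 81 cases = 46.9% (Section 4). Assumed: exactly 30 cancers, all biopsied, and everyone else unbiopsied BIRADS 1–3 with benign follow-up. Then biopsied = 30/yield, dropped = 100 − biopsied, benign biopsied = biopsied − 30. In all 70 non-cancers, work-up specificity = dropped/70. Among biopsied women it is 0 at every yield below.

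| Cancer yield of biopsy | Biopsied | Dropped | Benign biopsied | Work-up specificity, all 70 |
|---|---|---|---|---|
| 30% | 100 | 0 | 70 | 0% |
| 35% | 86 | 14 | 56 | 20.0% |
| 40% | 75 | 25 | 45 | 35.7% |
| 46.9% | 64 | 36 | 34 | 51.4% |
| 60% | 50 | 50 | 20 | 71.4% |
| 80% | 38 | 62 | 8 | 88.6% |

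**Mammography alone, at 46.9%.** Assume the mammogram was negative in 10% to 30% of the 34 benign biopsies (3 to 10 women) and in all 36 unbiopsied women.

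- Biopsied only: 3/34 = 8.8% to 10/34 = 29.4%.
- All non-cancers: (3 + 36)/70 = 55.7% to (10 + 36)/70 = 65.7%.

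**CE-CBBCT minus mammography.** Assume CE-CBBCT is negative in half of the benign biopsies (17/34). Biopsied only, the difference is (17 − 3)/34 = +41.2 points or (17 − 10)/34 = +20.6 points. In all 70 non-cancers:

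| CE-CBBCT negative in the 36 unbiopsied | Against 39 mammogram-negatives | Against 46 |
|---|---|---|
| 90% (32) | (17 + 32 − 39)/70 = +14.3 | (17 + 32 − 46)/70 = +4.3 |
| 75% (27) | (17 + 27 − 39)/70 = +7.1 | (17 + 27 − 46)/70 = −2.9 |
| 50% (18) | (17 + 18 − 39)/70 = −5.7 | (17 + 18 − 46)/70 = −15.7 |

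Varying the CE-CBBCT negatives among benign biopsies from 30% to 70% (10 to 24 of 34) gives (10 − 10)/34 = 0 to (24 − 3)/34 = +61.8 points biopsied only. In all non-cancers it gives (10 + 18 − 46)/70 = −25.7 to (24 + 32 − 39)/70 = +24.3 points.

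**McNemar's test.** Women negative on both tests do not enter the discordant counts, so dropping them changes the estimates but not the test. The discordant women who are dropped are CE-CBBCT positive and mammography negative: 4, 9 or 18 in the rows above. Net discordance in favour of CE-CBBCT is 17 − 3 = 14 among biopsied women, and 10, 5 or −4 with all non-cancers.

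A second example compares CE-CBBCT with the work-up call. Take 40 unbiopsied BIRADS 1–3 women and 30 benign biopsies, with CE-CBBCT specificity assumed to be 0.8 and 0.3 respectively. The statistic is (b − c)²/(b + c).

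- Biopsied only: discordant counts 0 and 9, difference 9/30 = +0.30, chi-square 81/9 = 9.0.
- All non-cancers: discordant counts 8 and 9, difference (32 + 9 − 40)/70 = +0.01, chi-square 1/17 = 0.06.

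The first is significant at the protocol's two-sided level; the second is not.

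**Sensitivity.** If follow-up shows 1 to 3 cancers that the work-up missed and that have no biopsy result in the analysis, work-up sensitivity is 30/31 = 0.97 to 30/33 = 0.91. The biopsy-only analysis reports 1.00.

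**The case against.** The strongest case on the other side accepts the mismatch in the text and disputes its consequences.

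- **The zero specificity belongs to the combined work-up call.** Section 9 scores each modality, and states no cut-off. Non-contrast CBBCT is itself a study scan, so selection by work-up does not act on it in the same way. This stands, and it is why mammography alone is worked separately.
- **CE-CBBCT findings have their own route to verification.** Sections 6, 12.1 and 14 provide for further work-up of findings seen only on CE-CBBCT, and biopsy may follow. This narrows the loss, and the illustration does not credit it. But referral does not always end in biopsy, so verification remains selective.
- **Percentage points overstate the effect on the test.** In the mildest case net discordance moves only from 14 to 10; much of the fall from +41.2 to +14.3 points comes from the denominator changing from 34 to 70. This is correct for that case. With more CE-CBBCT false positives among unbiopsied women, the test itself moves materially.
- **The analysis is not primary.** The only endpoint is acquisition, the McNemar step is conditional on enough data, and Section 1.2 argues for a representative database for the reader study, which is untouched. All true; this limits the severity. The sensitivity and specificity estimates are planned regardless.
- **Follow-up data may already be collected.** Section 6 promises information from additional work-up or biopsy arising from follow-up imaging, and the case report forms are not shown. So data capture is something to confirm, not an established gap.

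None of this reverses the direction of the bias against the work-up modalities.

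**Conclusion.** The concern holds. Section 9 states a reference standard that conflicts with Section 6.1 and, through its own available-case rule, removes unbiopsied BIRADS 1–3 women from the accuracy comparison. This is a rule that gives a biased answer as written, not a detail left to a later plan.

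The direction follows from the text, given that biopsy mostly follows a positive work-up. The size does not: every accuracy value above is assumed, as are the BIRADS ≥4 cut-off, the 30 biopsied cancers and the benign follow-up of everyone else. Under those assumptions the number lost runs from 0 to 62 of 100, and is 36 at the earlier trials' yield. At that yield, an apparent specificity gain over mammography can shrink, vanish or change sign.

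It should be fixed, but it does not threaten the trial. These women remain in the trial, the acquisition endpoint, the safety analysis and the separate multi-reader study.

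**What to change.** 1. **Section 9:** define the reference standard as pathology where obtained, and otherwise the follow-up result that Section 6.1 already accepts as final confirmation. Include every patient verified either way in the sensitivity and specificity denominators and in McNemar's test.
2. **Section 9:** report the biopsied-only results as secondary. Truth would then come from two sources of unequal certainty, and showing both sets lets the reader judge how much that matters. Report how many women were verified by each source.
3. **Section 9:** state how women with BIRADS 4 or above but no biopsy or surgery are handled. Section 6.1 gives them no reference result, so the change in item 1 does not by itself bring them in; at the least, count and report them.
4. **Section 6.3.3:** align the histology-only comparison with the same definition.
5. **Sections 7 and 8:** confirm that a case report form captures the follow-up outcome, and add an item if not.

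The cost is wording and possibly one form item; no extra patients are needed. The accuracy analysis must wait for follow-up, and the apparent specificity gain of CE-CBBCT may be smaller. The change mainly repairs specificity; sensitivity improves only as far as follow-up uncovers cancers.

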10 PATIENT CONFIDENTIALITY

The recruiting sites will be responsible for providing source documentation, such as images and reports. In order to minimize the use of PHI in communications between the study coordinator and recruiting sites, study packets, each with a unique study identifier, will be provided to each recruiting site. At recruitment, each volunteer is issued a study packet with a unique study identifier. Unused ID numbers will not be re-issued. The recruiting sites will keep a database that connects the subject name and medical record number with the unique study ID number. This computer will be password protected and locked down when user not engaged and accessible only

Clinical Trial Protocol			
Title:	Contrast-Enhanced Cone Beam Breast CT for Diagnostic Breast Imaging		
Internal #:	16-01		
IRB #:	RSRB00061893	NCT #:	NCT03354611
Revision:	3.5	Effective Date:	

to study personnel at recruiting sites. The primary computer databases will be established at the Highland Breast Imaging, and will connect the study ID number with the subject name and other demographics. These computers will be password protected and locked down when user not engaged and accessible only to study personnel.

A request for source documentation from recruiting sites, such as images and reports will be managed through study ID and subject initials.

In addition to study personnel directly involved with this clinical trial, only the University of Rochester, and the Department of Health and Human Services will have access to subject files for purposes of audit. CRO personnel and monitor will also have access to subject files for purposes of monitoring and audit.

De-identified images and data from this study may be used to apply for grants to support future studies, or may be used for other studies. In addition, the University of Rochester may license de-identified images and data to Koning Corporation, who has exclusive rights to market the CBBCT machine.

Any images used for evaluation or publication will be scrubbed of personal identifiers.

11 RESEARCH INFORMATION IN MEDICAL RECORDS

The following information will be included in the subject's electronic health record:

- Documenting participation
- A copy of the signed consent form
- Results of all testing done as part of this study

12 POTENTIAL RISKS OF THE STUDY

12.1 ADDITIONAL DIAGNOSTIC WORKUP

It is possible that the CE-CBBCT will detect an abnormality not previously evident by conventional imaging methods. This may lead to further focused imaging work-up, which may include ultrasound, mammography, or breast MRI. Biopsy or short-term follow-up may be recommended based on this additional work-up. The subject and her doctor will be informed of any new findings based on the CE-CBBCT. This added work-up might cause the subject undue anxiety and additional investment of time.

Clinical Trial Protocol			
Title:	Contrast-Enhanced Cone Beam Breast CT for Diagnostic Breast Imaging		
Internal #:	16-01		
IRB #:	RSRB00061893	NCT #:	NCT03354611
Revision:	3.5	Effective Date:	

12.2 RADIATION EXPOSURE

There will be radiation exposure to the breast(s) resulting from the CE-CBBCT study. The relationship between breast cancer and radiation has been studied extensively. It is known that female breast tissue is sensitive to ionizing radiation [16]. However, risk is highly influenced by previous radiation dose to the breast as there is a linear relationship between dose and risk, although the time intervals between exposures may reduce the cumulative effects. Of significant importance is the age at which exposure occurs. At high doses of 100cGy (1000 mGy), in a *young* woman, relative risk of developing breast cancer at a later age (typically 35-40 years later), is increased from 1.0 to 1.4 (2.0 would be double the risk), which is equivalent to the increase in risk from other factors, such as: nulliparity, early age at first menarche (under age 11 years), and having a very late age at menopause [16]. There is no proof of “*statistically significant increases below a dose of about 20 cGy (200 mGy)*” ... and further, “*for exposure after the age of about 45 years there is little evidence that radiation increases the occurrence of breast cancer*” [16]. The FDA mandates dose limits for screening mammography, because the benefit of screening mammography lies in the need for annual repeat exams to reap the benefits of early detection. The FDA sets a limit of 6 mGy for a two-view screening mammogram, for a 4.2 cm compressed breast with a 50/50 distribution of fat to glandular tissue [17]. The dose for a CBBCT scan to obtain a CNR of ~8, for a 4.2 cm breast equivalent phantom with a 50/50 distribution, is approximately 5.8 mGy. A CNR of ~8 has been determined to be the level needed for *diagnostic* adequacy (it is likely that screening dose will be more readily understood from the results of this study). There is no mandate that controls the dose for diagnostic mammography because the benefit/risk ratio is considerably higher in the diagnostic population. Also, the radiologist may require an unknown number of extra mammographic views in order to make a diagnostic decision. The American College of Radiology and the Radiologic Society of North America equates the effective whole body dose of a mammographic exam (0.7 mSv) to about 3 months of background radiation [18].

Analysis based on data from 220 diagnostic patients, which are representative of the range of breast thicknesses and densities found in a female population, has shown that the average mean glandular dose of one CBBCT scan and one diagnostic mammography exam is 10.6 mGy (standard deviation 3.89) and 9.57 mGy (standard deviation 5.16), respectively. The overall dose range is comparable and the dose values are less variable for the CBBCT [14].

The CBBCT study includes two low dose scout images, acquired at a standard dose (~0.30 each for the two images; 0.6 mGy total), and the CBBCT scan. For the CBBCT scan, we propose delivering the *minimal* average glandular dose level required to maintain sufficient image quality for each subject. The dose from the CBBCT scan varies with breast size and density and is determined for each individual breast from the two low-dose scout images. Dose from the CBBCT scan will range from ~4 mGy to no more than ~16 mGy (+/- 20%) (depending on breast size and density) to provide a CNR of ~8, the level needed for diagnostic adequacy. The amount of radiation exposure from one CBBCT scan of one breast is equivalent to an effective whole body dose of ~0.6 - 1.9 mSv. Thus, the highest dose from the CBBCT of 1.9 mSv would approximate the same dose received from about 7

Clinical Trial Protocol			
Title:	Contrast-Enhanced Cone Beam Breast CT for Diagnostic Breast Imaging		
Internal #:	16-01		
IRB #:	RSRB00061893	NCT #:	NCT03354611
Revision:	3.5	Effective Date:	

½ months of background radiation. The CBBCT dose is within the range of what could be expected from diagnostic mammography studies.

The dose range of the CBBCT study is substantially less than the minimum dose recognized to induce an increased risk for breast cancer. In addition, we will institute a data safety and monitoring plan for this study to assure that dose remains within the stated limits, while continuously evaluating image quality along with improvements that may reduce the dose of the CBBCT study.

For CE-CBBCT exam (one pre- and one post-contrast) the dose and associated risk increases linearly by the number of scans. The dose from a CE-CBBCT exam of one breast is ~8mGy to ~32mGy (+/- 20%) (depending on breast size and density). The amount of radiation exposure from one CE-CBBCT exam of one breast is equivalent to an effective whole-body dose of 1.2 mSv to 3.8 mSv, which is equivalent to approximately 4.6 months to 14.7 months of natural background radiation. This conversion is based on a breast tissue weighting factor of 0.15 per NRC 10CFR 20.1003 Definitions. In addition, this is meant to be a one-time study, not a periodic screening routine.

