mGy to ~13 mGy per scan, depending on breast size and density, or similar to the subject's diagnostic mammogram. In this study, the dose for a full two-scan contrast imaging will be ~ 8 to 32 mGy, or similar to two diagnostic mammography exams.

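### The protocol states two maximum doses for the same scan (~13 and ~16 mGy), and Section 12.2's upper mSv figures do not follow from its own mGy figures

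*Protocol*

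**What the plan says.** Section 6.1 fixes the tube current ("The mA will be automatically selected by the CBBCT system from 50 to 160 mA") and converts it to a per-scan glandular dose of about 4 "mGy to ~13 mGy per scan, depending on breast size and density". Its next sentence gives 8 to 32 mGy for two scans. Section 6.3.1 gives 4 to 13 mGy per scan (±20%), 8 to 26 mGy for two scans, and an effective dose of 0.12 to 3.8 mSv at a weighting factor of 0.15, equated to 4.6 to 14.7 months of background radiation.

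Section 12.2 gives different upper ends. One scan ranges from about "4 mGy to no more than ~16 mGy (+/- 20" per cent), said to be "equivalent to an effective whole body dose of ~0.6 - 1.9 mSv". For the two-scan exam: "The dose from a CE-CBBCT exam of one breast is ~8mGy to ~32mGy (+/- 20" per cent), "equivalent to an effective whole-body dose of 1.2 mSv to 3.8 mSv". The basis is stated: "This conversion is based on a breast tissue weighting factor of 0.15 per NRC 10CFR 20.1003 Definitions". The same section announces a monitoring plan "to assure that dose remains within the stated limits".

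Section 12.4 (machine failure) uses 4 to 16 mGy for a repeated scan and 12 to 48 mGy in total.

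**The concern.** The same scan, on the same machine with the same current limit, has two stated maxima. Section 6.1 disagrees with itself from one sentence to the next, since two scans of at most 13 mGy cannot reach 32 mGy. Within 12.2, the conversion to effective dose works at the lower ends of the ranges and fails at the upper ends.

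Section 12.2 is where the protocol describes the radiation risk to participants, and it promises to hold doses within stated limits. A reader cannot tell which upper limit is meant, or whether 3.8 mSv is the true maximum or an understatement.

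**Working it through.** **Formula.** Effective dose (mSv) = glandular dose (mGy) × breast tissue weighting factor. Sections 6.3.1 and 12.2 both state the factor as 0.15. The statement in 12.2 is attached to the two-scan exam. The single-scan lower end implies the same factor: 0.6 / 4 = 0.15.

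**Step 1: Section 12.2's own figures.**

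| Section 12.2 dose | × 0.15 | × 0.12 | Printed |
|---|---|---|---|
| 4 mGy | 0.60 | 0.48 | 0.6 |
| 16 mGy | 2.40 | 1.92 | 1.9 |
| 8 mGy | 1.20 | 0.96 | 1.2 |
| 32 mGy | 4.80 | 3.84 | 3.8 |

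At 0.15 the lower ends reproduce and the upper ends do not. At 0.12, the factor used in Section 1.2, the reverse holds. No single factor converts the printed mGy ranges into the printed mSv ranges.

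**Step 2: which doses give the printed mSv at 0.15.** 1.9 / 0.15 = 12.7 mGy and 3.8 / 0.15 = 25.3 mGy. These sit beside the 13 and 26 mGy of 6.3.1 (13 × 0.15 = 1.95; 26 × 0.15 = 3.9), not beside 16 and 32.

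**Step 3: sums over scans.**
- Two scans: 2 × 13 = 26 (6.3.1); 2 × 16 = 32 (12.2, and the second sentence in 6.1).
- Three scans: 3 × 13 = 39; 3 × 16 = 48 (12.4).

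**Step 4: the tolerance.** 13 × 1.2 = 15.6, 26 × 1.2 = 31.2 and 39 × 1.2 = 46.8, each just short of 16, 32 and 48. But 12.2 attaches ±20% to 16 and 32 again, which would allow 16 × 1.2 = 19.2 and 32 × 1.2 = 38.4.

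**Step 5: a possible origin.** Assume dose is proportional to mA. Then 4 mGy at 50 mA is 0.08 mGy per mA, so 160 mA gives 12.8 mGy and 200 mA gives 16.0 mGy. The first converts to 12.8 × 0.15 = 1.92 mSv, and two such scans to 25.6 × 0.15 = 3.84 mSv, matching the printed values. The revision history records a change of the limit from 200 to 160 mA, so 16, 32 and 48 mGy may be values left from the old limit. This explains the figures; the contradiction does not depend on it.

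**Step 6: background equivalents if 16 mGy is right.** Section 12.2's own rate is 3.8 / 14.7 = 0.2585 mSv per month.
- Exam: 4.8 / 0.2585 = 18.6 months, against 14.7 printed.
- One scan: 2.4 / 0.2585 = 9.3 months, against about 7.5 printed.

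The protocol's other equivalences imply annual rates from 2.8 mSv (0.7 mSv per 3 months, Section 12.2) to 3.5 mSv (7 mSv per 2 years, Section 6.3.1). Over that range the exam equals 16.5 to 20.6 months and one scan 8.2 to 10.3.

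**Step 7: the lower end in 6.3.1.** 8 × 0.15 = 1.2 mSv, and 1.2 / 0.2585 = 4.6 months, as printed there. The printed 0.12 mSv would be 0.46 months, so it is a decimal slip.

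**The case against.** The best defence is that 13 mGy is nominal and 16 mGy is the ceiling after adding 20%: 15.6 rounds to 16, doubling and tripling give 32 and 48, and the mSv figures are quoted at nominal. All the values are approximate, and this fits most of them. It fails because 12.2 adds ±20% to 16 and 32 once more, leaves the lower ends at the nominal 4 and 8, and presents the mSv range as the equivalent of the mGy range beside it.

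A second objection is that proportionality to mA is doubtful as a way of choosing between the maxima: mA is set by breast size and density, so the two ends of the range are different breasts. The protocol's patient data (mean 10.6 mGy, SD 3.89, 220 patients) would, under a normal approximation, put about 27% of scans above 13 mGy and 8% above 16 mGy. It is not stated whether those scans were made under the 160 mA limit, so they do not settle the matter, but they are a reason not to assume 13 mGy without checking.

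Third, little hangs on the error. On the likelier reading exposure is overstated, so nobody is told of less radiation than she receives. All maxima, including 48 mGy, are far below the 200 mGy cited in 12.2. The check in Section 13 compares actual doses with a radiation committee application that is not shown, so no effect on monitoring can be claimed. All of this stands. It limits the consequence without removing the contradiction.

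**Conclusion.** The dose figures are wrong as written: 13 and 16 mGy cannot both be the per-scan maximum, and 1.9 and 3.8 mSv are not 16 and 32 mGy at 0.15. This follows from the current text alone.

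The size depends on which maximum is true.
- **About 13 mGy** (likelier, mainly because the printed mSv values convert back to it at the stated factor): 16, 32 and 48 mGy are 23% too high (16 / 13 = 1.23), and the upper mSv figures stand to rounding.
- **About 16 mGy**: 1.9 and 3.8 mSv should be 2.4 and 4.8 mSv, 26% higher (4.8 / 3.8 = 1.26), and the background months rise accordingly. The alternative that 12.2's upper ends were computed at 0.12 cannot be excluded, though its lower ends contradict it.

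The 0.12 mSv in 6.3.1 is wrong on either reading. Section 12.2's risk conclusion, the sample size, the endpoint and the analysis are unaffected.

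**What to change.** Confirm the per-scan maximum at 160 mA and use it in Sections 6.1, 6.3.1, 12.2 and 12.4.

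- If it is about 13 mGy, print 13, 26 and 39 mGy for one, two and three scans, and keep about 1.9 and 3.8 to 3.9 mSv.
- If it is about 16 mGy, print 16, 32 and 48 mGy with 2.4 and 4.8 mSv, and recompute the background months.
- In either case, change 0.12 to 1.2 mSv in 6.3.1, and say once whether ±20% applies on top of the stated maximum.
- Optionally, use 0.15 in Section 1.2 too. Its 1.39 mSv is correct at its stated 0.12 (11.6 × 0.12); at 0.15 it becomes 11.6 × 0.15 = 1.74 mSv, with the months figure recomputed.

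The cost is one technical check and an edited set of numbers, with no change to procedures, sample size or analysis. The downside is that, if 16 mGy is confirmed, the exposure stated for participants rises from 3.8 to 4.8 mSv.
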